## 6.0 Procedures Involved

### Study Design

The study is an unblinded, 3-arm, randomized, controlled trial. After successful screening and consent, individuals will wear a blinded Dexcom G6 Pro CGM inserted 1 week after consent. Families who have previously used a CGM device

will be allowed to insert the G6 Pro during a remote visit. At the baseline visit (visit 1; day 1), participants will be randomized to the COIN2DOSE, LOAN2DOSE, or control treatment arms and will be trained on the procedures appropriate to their treatment arm. Participants will also complete baseline measures by questionnaire. Participants will complete procedures specific to their treatment arm weekly. Visit 2 will occur after 12 weeks (90 days). Participants will stop any treatment interventions after this visit. A1C and questionnaire measures will be completed, and participants will again wear the Dexcom G6 Pro CGM for 10 days (the device will be returned by mail post-visit). Participants will receive no treatment intervention from week 13 to week 24. Visit 3 will occur after week 24. Again, A1C and questionnaire measures will be completed and participants will wear the Dexcom G6 Pro CGM for 10 days. Participants who have their own CGM will wear it as usual and will not require a blinded Dexcom.

All study participants will also have the option to participate in a focus group discussion (FGD) regarding study participation.

Parents of children who meet inclusion criteria and participate in the study may also elect to participate in a focus group.

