## 10.0 Study Timelines

Table 1. Schedule of events

visit #	Visit 1	CGM placement	Intervention	Visit 2	Maintenance	Visit 3
		1 week post enrollment	1-12 week post CGM placement	3 months (+/-14 days)	12 weeks post visit 2	6 months (+/-14 days)
Consent	x					
Randomization	x					
CGM (10-day)		x*		x*		x*
A1C	x			x		x
Demographic	x			x		x
PHQ9	x			x		x
DTSQteen	x			x		x
MyQ	x			x		x
Wake Forest Physician Trust Scale	x			x		x
Perceived Involvement in Care Scale	x			x		x
Health-related empowerment scale.	x			x		x
Concerns about AI	x			x		x
Pump/pen** download	x		x	x	x	x
Focus Group Participation - Youth						x
Focus Group Participation - Parents						x

\*CGM will be returned by pre-paid, registered delivery service with tracking.

\*\* Control: pump/pen upload will occur monthly; COIN2DOSE and LOAN2DOSE pump/pen upload will occur twice weekly.

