## 11.0 Inclusion and Exclusion Criteria

Individuals who have been predicted via an artificial intelligence-intelligence based model to experience a rise in A1C in the near future (90 days) will be approached for recruitment. 36 participants will be recruited from the Children's Mercy Diabetes Center (any clinic or hospital location). Based on preliminary data review of our clinic population, there were at least 81 individuals who met inclusion criteria who were seen in clinic in the month of May 2019 alone. Patients will be randomized to, COIN2DOSE, LOAN2DOSE, or control group using a 1:1:1 randomization scheme.

Inclusion Criteria:

- 1) Aged 12-17.99 years
- 2) The youth must have been diagnosed with T1D for at least 6 months
- 3) The youth must have attended at least 2 routine T1D standard of care visits in the past 12 months

- 4) The youth must be using an insulin delivery device capable of recording, storing, and downloading insulin bolus behaviors (insulin pump or smart Bluetooth insulin pen that can be uploaded to standard clinic upload software).
- 5) The youth must have a current A1C >7.2% and/or be predicted to have a rise in A1C in of 0.3% or higher the next 90 days.
- 6) Not pregnant or planning to become pregnant by self-report.

Exclusion Criteria:

- 1) Participants with any type of diabetes mellitus other than T1D
- 2) Participant has any disease-causing anemia or affecting red blood cell physiology (which would impact A1C)
- 3) Participant has a physical disability, which in the opinion of the investigator would interfere with individual's ability to feed themselves or use one's hands to facilitate eating
- 4) Participants with no internet access or ability to upload device(s) to data aggregation software that is accessible to study team.

For Focus Groups:

Any parent or legal guardian whose child is participating in the study is invited to participate in a focus group discussion.

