## **16.0 Withdrawal of Subjects**

Participants may withdraw from the study at any time and this will not affect their medical care. No additional study related data will be collected on participants after withdrawal from the study, but previously collected information will be retained. All participants who enroll into the study will be included in the primary analysis, with the exception of those who are withdrawn from the study for not meeting eligibility criteria.

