## 20.0 Data Management and Confidentiality

### 20.1 Statistical Analysis Plan

Database construction and management will involve acquisition of data from each source (see above), imported into Microsoft Excel or an equivalent database program. All analysis will be completed using Stata/SE 15.1 (StataCorp. 2017. Stata Statistical Software: Release 15. College Station, TX: StataCorp LLC), SPSS version 20, SAS version 9.4, other statistical programs as needed. Univariate analysis will be performed on all dependent and independent variables. Analysis includes determining whether the variables have non-normal distributions or outliers. Determinations then will be made as to whether the data transformations are needed. For example, if variance heteroscedasticity, exists, data will be analyzed using log-transformed or other transformations based upon Box-Cox approximations to normal distributions. Measures of other central dependency and dispersion will be evaluated. Primary analyses will be modified intention to treat analysis. All individuals who are randomized will be included in the analysis. A secondary per-protocol analysis may also be performed. Multivariable regression models will be examined to estimate the effects of study variables on the primary outcome – predicted trajectory of glycemic control base on A1C over 90 days – for this sample of T1D patients' data collected at three time points: baseline, 3 months, and 6 months. If the independent variables are highly correlated, we will explore General Linear Models (GLM) or other models. It is possible that Generalized Estimating

Equations (GEE) will be explored for their appropriateness in a larger study and/or for comparisons with the GLM results. Demographic and clinical variables will be entered into models following the independent variable: treatment group assignment. Since time effects may be important in the analyses due to treatments, censoring of data, time sequences, or other reasons, time of observation (i.e. visit 1[day 0], visit 2 [day 90], or visit 3 [day 180]) will also be explicitly accounted for in the regression models. All models will account for the clustering effect of participants having more than one clinic visit during the study timeframe. Additional variables will be collected as listed above. Statistical significance will be  $p<0.5$  (one-sided).

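### Sections 16.0 and 20.1 define the primary analysis set differently, and the eligibility exception is not tied to pre-randomisation facts or to judgement made without knowledge of arm

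*Protocol*

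**What the plan says.** The protocol defines the primary analysis set in two places.

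- **Section 20.1** gives a label, "Primary analyses will be modified intention to treat analysis", and then the content: "All individuals who are randomized will be included in the analysis". It does not say what the modification is.
- **Section 16.0** uses a different base, "All participants who enroll into the study will be included in the primary analysis", and attaches an exception: "with the exception of those who are withdrawn from the study for not meeting eligibility criteria".

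Four other places bear on how the exception would work.

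- **Section 6.0, Study Design:** "The study is an unblinded, 3-arm, randomized, controlled trial". On timing it says: "At the baseline visit (visit 1; day 1), participants will be randomized to the COIN2DOSE, LOAN2DOSE, or control treatment arms".
- **Section 10.0:** Table 1 marks consent and randomisation in the same Visit 1 column. The participant activities table also has participants enrolled and randomised at one step.
- **Section 11.0:** exclusion 3 depends on the investigator's opinion about a physical disability. Exclusion 4 reads: "Participants with no internet access or ability to upload device(s) to data aggregation software that is accessible to study team".
- **Section 10.0, footnote to Table 1:** "COIN2DOSE and LOAN2DOSE pump/pen upload will occur twice weekly", whereas control uploads are monthly.

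**The concern.** An all-randomised set and a set that drops people withdrawn as ineligible coincide only if nobody is found ineligible after randomisation. If someone is, the analyst must choose between two protocol rules for the primary comparison, and may do so with outcomes already visible.

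Removing ineligible participants can be harmless when the facts were fixed before randomisation and are judged by people who do not know the arm. Section 16.0 sets neither condition. Staff know the allocation, and some criteria can be assessed or reassessed later. Exclusion could then depend on arm and, through engagement, on outcome. With 12 to 24 participants per arm, one or two such decisions could visibly move the primary A1C comparison.

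**Working it through.** **Step 1. The two rules side by side**

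| | Section 20.1 | Section 16.0 |
|---|---|---|
| Base | randomised | enrolled |
| Exception | none | withdrawn as ineligible |
| Time limit on the exception | not applicable | none stated |
| Judged without knowledge of arm | not applicable | not stated |

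Take a youth who is randomised and then withdrawn as ineligible. Section 20.1 keeps that youth and Section 16.0 removes them. The modified label does not settle it, because the sentence that follows the label admits no exception.

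**Step 2. Can timing remove the conflict?**

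The rules agree if every eligibility withdrawal falls between consent and randomisation. Section 6.0 can be read as leaving such a gap, since it describes screening and consent, then a sensor one week after consent, then randomisation at the baseline visit. Section 10.0 places consent and randomisation at one visit with the sensor a week later, which leaves almost no gap. No section says that eligibility withdrawals stop at randomisation.

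**Step 3. Routes by which exclusion could differ by arm**

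- Exclusion 3 is a judgement by an investigator who knows the arm.
- Exclusion 4 concerns the ability to upload. Uploads are twice weekly in COIN2DOSE and LOAN2DOSE and monthly in control, so a problem has more occasions to come to light in the active arms.

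**Step 4. Illustrative upper bound**

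The protocol gives no figure to reproduce here.

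Inputs:
- Section 13.0 has a target of 36 and a maximum of 72. With 1:1:1 allocation, that is 36/3 = 12 or 72/3 = 24 per arm.
- Assumptions: no true effect, normal outcomes with SD 1, and the participants deleted are exactly those with the worst A1C change in one active arm.

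If the largest of n values is removed, the expected shift in the arm mean is E[max]/(n − 1). For n = 12, E[max] is about 1.63, so the shift is 1.63/11 = 0.148 SD in the direction of apparent benefit.

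A simulation (200,000 runs, equal-variance t-test of one active arm against control, nominal one-sided level 0.025) gave:

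| Per arm | Deleted | Shift (SD) | One-sided error |
|---|---|---|---|
| 12 | 0 | 0.000 | 0.026 |
| 12 | 1 | 0.148 | 0.060 |
| 12 | 2 | 0.274 | 0.107 |
| 24 | 0 | 0.000 | 0.025 |
| 24 | 1 | 0.084 | 0.052 |
| 24 | 2 | 0.157 | 0.087 |

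The 20 per arm used in Section 20.2 lies between these, with a shift of 0.098 SD for one deletion.

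The protocol states no SD for A1C change, so 0.6 to 1.0% is assumed. For one deletion:
- 12 per arm: 0.148 × 0.6 = 0.09% to 0.148 × 1.0 = 0.15%.
- 24 per arm: 0.084 × 0.6 = 0.05% to 0.084 × 1.0 = 0.08%.

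**The case against.** The strongest reply is that the sections can be reconciled. Section 20.1 announces a modified intention to treat analysis, and Section 16.0 supplies the only candidate modification in the document. Alternatively, enrolment may precede randomisation, so that the exception acts only before allocation. Either may be what was meant. Neither is stated: the sentence after the label contradicts the first reading, and Table 1 sits badly with the second.

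A reader might go further and infer that ineligible participants will be found more often in the active arms, and that the primary result will therefore favour them. The protocol does not support that.
- Exclusion 4 is about capability at screening, not about uploading behaviour.
- Inclusion 4 already requires an uploadable device, and Table 1 schedules a download at Visit 1 in every arm.
- Section 5.0 gives failure to share data its own consequence: up to $2.00 a week is not earned in COIN2DOSE or is deducted in LOAN2DOSE.
- No section withdraws a participant for not uploading.

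The upload route is thus a possibility left open by the wording, and no more. The argument is weaker still for the BOLUS score, which is built from uploaded data. A youth who cannot upload would largely lack that score whichever set is used.

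It is also fair to say that this is a pilot looking for a preliminary trend, that the calculation takes the worst case, and that details of analysis sets often sit in a SAP. The last point does not dispose of the matter, because the protocol itself fixes the primary set twice and differently.

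**Conclusion.** The inconsistency is real and concerns the primary analysis. What is established is that two definitions stand in the current text, that they diverge once a randomised participant is withdrawn as ineligible, and that no safeguard ties the exception to pre-randomisation facts or to judgement made without knowledge of arm. Arm-dependent exclusion is permitted, not prescribed, and its direction cannot be predicted from the document.

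The shifts of about 0.15 SD at 12 per arm and 0.08 SD at 24 per arm are ceilings for one deletion. They assume that the person removed has the worst outcome and that only one arm loses anyone. Exclusions unrelated to arm and outcome would cause no such bias. The A1C equivalents rest on an SD that the protocol does not give. The point deserves correction because the samples are small and the remedy is cheap; it does not by itself invalidate the design.

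**What to change.** - In Sections 16.0 and 20.1, define the primary set in the same words: all randomised participants, analysed in the arm to which they were assigned. Remove the exception from Section 16.0, and either drop the modified label or say what it means.
- Move the exclusion of ineligible participants to a sensitivity analysis. Limit it to facts fixed before randomisation, judged by people unaware of arm and outcome.
- State that failure to upload after randomisation does not count as ineligibility for analysis.

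The cost is wording in two sections, plus slight dilution of any effect if a few truly ineligible youth stay in. A modified set built only on pre-randomisation facts judged without knowledge of arm could also be defended as primary, provided it is defined and accompanied by the all-randomised analysis. The all-randomised set is simpler and matches what Section 20.1 already promises.

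One limit remains. Section 16.0 ends study data collection at withdrawal, so a redefined set cannot recover a 90-day A1C that was never obtained.

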## **17.0 Risks to Subjects**

The overall risks of participation in this project are no more than minimal. Because the research requires the collection of personally identifying data, there is a risk breach of confidentiality. Participants will be requested to disclose information about their diabetes adherence, blood glucose values, regimen knowledge, and psychological and behavioral functioning. Disclosing this information may potentially lead to emotional discomfort. If a participant reports any concerning symptoms regarding his or her emotional stature, the participants and his/her parent/guardian will be provided with information on how to get help. If a participant has a positive screen on the PHQ-A (depression), social work will be notified and will see the participant during the study visit. Social work will assess the patient and develop a plan of action in conjunction with the attending physician based on the clinical situation. Participants may also feel inconvenienced by the time required to participate in the study. Participants may

experience some discomfort with Dexcom insertion, which is similar to insulin pump site insertions. Participants will be instructed on proper care of the Dexcom site.

In the virtual focus group discussions, there is minor risk of unauthorized disclosure of confidential information, which would be made known to participants and will be minimized by the research team's efforts to ensure confidentiality (see section 20.0). Every effort will be made to keep data de-identified, including having participants use pseudonyms for the discussion and being reminded not to respond in a way that might include personal identifying information. Risks are greatly reduced by using secure files, storing data on secure computers, de-identification of data. Subjects and/or their parents/legal guardians may choose not to participate in the focus groups. There may be a risk that some of the questions make participants feel uncomfortable. Participants may skip a question or stop the study at any time.

## **18.0 Potential Benefits to Subjects**

Participants could benefit by responding to the financial incentives (COIN2DOSE or LOAN2DOSE) and improve their mealtime dosing behaviors. With improved insulin dosing behaviors, the participants may improve their overall glycemic control. It is possible that participants will not derive any benefit from participation.

Parents/legal guardians who choose to participate in the focus group may or may not gain useful information to help their child improve diabetes care. It is possible that parents/legal guardians will not derive any benefit from participation.

## 19.0 Investigator Assessment of Risk/Benefits Ratio: (IRB makes the final determination)

Select as applicable:	Pediatric Risk Category:	
	Category 1	Research not involving greater than minimal risk (45 CFR §46.404 and 21 CFR §50.51)
	Category 2	Research involving greater than minimal risk but presenting the prospect of direct benefit to the individual subjects. (45 CFR §46.405 and 21 CFR §50.52)
	Category 3	Research involving greater than minimal risk and no prospect of direct benefit to individual subjects, but likely to yield generalizable knowledge about the subject's disorder or condition. (45 CFR §46.406 and 21 CFR §50.53)
	Category 4	Research not otherwise approvable which presents an opportunity to understand, prevent, or alleviate a serious problem affecting the health or welfare of children. (45 CFR §46.407 and 21 CFR §50.54)
Select if applicable:	Adult Risk Category:	
	Not Greater than Minimal Risk	
	Greater than Minimal Risk	

## 20.0 Data Management and Confidentiality

### 20.1 Statistical Analysis Plan

Database construction and management will involve acquisition of data from each source (see above), imported into Microsoft Excel or an equivalent database program. All analysis will be completed using Stata/SE 15.1 (StataCorp. 2017. Stata Statistical Software: Release 15. College Station, TX: StataCorp LLC), SPSS version 20, SAS version 9.4, other statistical programs as needed. Univariate analysis will be performed on all dependent and independent variables. Analysis includes determining whether the variables have non-normal distributions or outliers. Determinations then will be made as to whether the data transformations are needed. For example, if variance heteroscedasticity, exists, data will be analyzed using log-transformed or other transformations based upon Box-Cox approximations to normal distributions. Measures of other central dependency and dispersion will be evaluated. Primary analyses will be modified intention to treat analysis. All individuals who are randomized will be included in the analysis. A secondary per-protocol analysis may also be performed. Multivariable regression models will be examined to estimate the effects of study variables on the primary outcome – predicted trajectory of glycemic control base on A1C over 90 days – for this sample of T1D patients' data collected at three time points: baseline, 3 months, and 6 months. If the independent variables are highly correlated, we will explore General Linear Models (GLM) or other models. It is possible that Generalized Estimating

Equations (GEE) will be explored for their appropriateness in a larger study and/or for comparisons with the GLM results. Demographic and clinical variables will be entered into models following the independent variable: treatment group assignment. Since time effects may be important in the analyses due to treatments, censoring of data, time sequences, or other reasons, time of observation (i.e. visit 1[day 0], visit 2 [day 90], or visit 3 [day 180]) will also be explicitly accounted for in the regression models. All models will account for the clustering effect of participants having more than one clinic visit during the study timeframe. Additional variables will be collected as listed above. Statistical significance will be  $p<0.5$  (one-sided).

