## 4.0 Study Endpoints

### Outcome Measures

Primary outcome:

- 1) Change in A1C ( $\Delta A1C_{90\text{-day}}$ ) from baseline visit (visit 1) to 90-day visit (visit 2).

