## Secondary outcomes:

- 1) Change in A1C ( $\Delta A1C_{180\text{-day}}$ ) from baseline visit (visit 1) to 180-day visit (visit 3).
- 2) Change in percent time in range 70-180 mg/dL (%TIR70-180) from baseline visit (visit 1) to 90-day visit (visit 2) and to 180-day visit (visit 3).
- 3) Change in percent time hyperglycemic ( $>180$  mg/dL; %Hyper>180) from baseline visit (visit 1) to 90-day visit (visit 2) and to 180-day visit (visit 3).
- 4) Change in percent Time hypoglycemic ( $<70$  mg/dL; %Hypo<70) from baseline visit (visit 1) to 90-day visit (visit 2) and to 180-day visit (visit 3).
- 5) Change in percent Time severely hypoglycemic ( $<54$  mg/dL) (%Hypo<54) from baseline visit (visit 1) to 90-day visit (visit 2) and to 180-day visit (visit 3).
- 6) Change in mealtime insulin BOLUS score (BOLUS) from baseline visit (visit 1) to 90-day visit (visit 2) and to 180-day visit (visit 3).
- 7) For COIN2DOSE treatment group, proportion of participants who complete  $>90\%$  of study procedures throughout the intervention and post-intervention study procedures.
- 8) For COIN2DOSE treatment group, proportion of parents who endorse the feasibility of providing an economic incentive equivalent to that used in the intervention.
- 9) For COIN2DOSE treatment group,  $>75\%$  of participants will exhibit a score of  $>80\%$  total possible points on Diabetes Treatment Satisfaction Questionnaire (teen version)
- 10) Change in trust in provider from baseline visit (visit 1) to 90-day visit (visit 2) and to 180-day visit (visit 3).
- 11) For LOAN2DOSE treatment group, proportion of participants who complete  $>90\%$  of study procedures throughout the intervention and post-intervention study procedures.
- 12) For LOAN2DOSE treatment group, proportion of parents who endorse the feasibility of providing an economic incentive equivalent to that used in the intervention.
- 13) For LOAN2DOSE treatment group,  $>75\%$  of participants will exhibit a score of  $>80\%$  total possible points on Diabetes Treatment Satisfaction Questionnaire (teen version)
- 14) Change in perceived involvement in care from baseline visit (visit 1) to 90-day visit (visit 2) and to 180-day visit (visit 3).
- 15) Change in health-related empowerment from baseline visit (visit 1) to 90-day visit (visit 2) and to 180-day visit (visit 3).

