### *20.2 Power analysis*

To evaluate the primary outcome: glycemic control (measures as predicted trajectory of A1C over 90 days), a multivariable regression model will be developed that accounts for seven independent variables: two primary – adherence and quality of life – and an additional five covariates: participant age, sex, insurance status, intervention/control group status, and time (52). Using an F-test and significant level (alpha) of 0.025, a sample of 20 T1D patients per treatment arm would achieve 74% power to detect an effect size of 0.35 (53). Findings from this pilot study will be used as estimates in planning future studies including recruitment of enough patients to achieve a power of greater than or equal to 80% to evaluate glycemic control (54).

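### The 90-day primary outcome is tied to three-visit data, and its only predictor list has no group-by-time term and names no visit-2 contrast, so the listed group coefficient is not the 90-day effect

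*Protocol*

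**What the plan says.** - **Outcomes (section 4.0).** The primary outcome is the A1C change between visit 1 and the 90-day visit 2. The change to the 180-day visit 3 is a separate secondary outcome.
- **Hypotheses (section 2.2).** Hypotheses 1 and 5 concern the rise in A1C against control. Hypotheses 3 and 7 concern persistence for 12 weeks after the intervention.
- **Analysis (section 20.1).** The primary outcome is described as "predicted trajectory of glycemic control base on A1C over 90 days", yet the regression uses "data collected at three time points: baseline, 3 months, and 6 months". Time of observation (day 0, 90 or 180) "will also be explicitly accounted for in the regression models", and clustering within participant is to be handled.
- **Predictors (section 20.2).** For the same outcome, "a multivariable regression model will be developed that accounts for seven independent variables": adherence, quality of life, age, sex, insurance, and then "intervention/control group status, and time".
- **Treatment periods (section 6.0, Study Design).** Randomisation takes place at visit 1 and the interventions end after visit 2. "Participants will receive no treatment intervention from week 13 to week 24".

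**The concern.** A 90-day outcome needs no month-6 data. If month 6 is in the model, the model needs a term that lets the arm difference vary by visit, and the plan must say which contrast is the 90-day effect. Sections 20.1 and 20.2 do neither. With one group term and one time term, the group coefficient is a weighted average of the arm differences at three visits: before treatment, at the end of treatment, and 12 weeks off treatment.

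Section 3.2 and section 20.2 both say that the pilot's estimates will be used to plan a definitive trial. An effect read from the wrong coefficient would carry through to that trial's sample size, or could cause a promising arm to be dropped.

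**Working it through.** **The plan's own figure.** The protocol gives no expected value for the group coefficient, so there is none to reproduce. Its 74% power (section 20.2) is not an input here. The plain readings at alpha 0.025 do not return it: a one-way ANOVA with f = 0.35 and 3 × 20 participants gives 54%, and f² = 0.35 with N = 60 and all seven variables tested gives 84%.

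**Inputs from the protocol.** There are three visits. The expected arm difference at visit 1 is 0, because participants are randomised there. The difference at visit 2 is D, the primary effect. The difference at visit 3 is kD, off treatment.

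**Assumed inputs.** k lies between 0 and 1. The within-person correlation rho is taken as 0.3 to 0.7. The protocol gives neither for A1C. Adherence and quality of life are left out of the calculation.

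**Step 1: A1C level as outcome, single group term, equal visit weights** (independence or compound symmetry; time categorical or linear gives the same result).

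Coefficient = (0 + D + kD)/3 = D(1+k)/3.

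| k | Coefficient |
|---|---|
| 0 | 0.33D |
| 0.5 | 0.50D |
| 1 | 0.67D |

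A simulation with 12 per arm and rho = 0.7 (400 trials per k, GEE with group and time) gave 0.31D, 0.53D and 0.66D. A baseline-adjusted visit-2 contrast gave 1.01D.

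For a sense of k, section 3.2 cites a trial in which an adherence difference of 27.2% during incentives fell to 3.9% afterwards: 3.9/27.2 = 0.14. If A1C behaved the same way, which is an assumption because that outcome was glucose monitoring, the coefficient would be 1.14D/3 = 0.38D.

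**Step 2: other readings of the same list.**
- Change from baseline at visits 2 and 3 as outcome: (D + kD)/2, or 0.50D to 1.00D.
- A1C level with AR(1) correlation: the visit weights are (1, 1−rho, 1)/(3−rho). At rho = 0.5 these are 0.4, 0.2 and 0.4, giving 0.20D to 0.60D. At rho = 0.7 the range is 0.13D to 0.57D.

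Of these readings, only change scores with full persistence return D.

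**Step 3: efficiency.** Under compound symmetry the per-participant variance is s²(1+2rho)/3 for the three-visit mean and s²(1−rho²) for the baseline-adjusted visit-2 value. The sample needed, as a multiple of that for the visit-2 contrast, is

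[9/(1+k)²] × [(1+2rho)/3] / (1−rho²).

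| rho | Variance ratio | k = 1 (× 2.25) | k = 0 (× 9) |
|---|---|---|---|
| 0.3 | 0.533/0.91 = 0.586 | 1.3 | 5.3 |
| 0.5 | 0.667/0.75 = 0.889 | 2.0 | 8.0 |
| 0.7 | 0.80/0.51 = 1.569 | 3.5 | 14.1 |

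These multiples combine the dilution with the precision gained or lost by adjusting for baseline; they do not measure dilution alone.

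**Step 4: planning the next trial.** With the SD unchanged, using an effect of one third to two thirds of D multiplies the planned sample by 1/(1/3)² = 9 down to 1/(2/3)² = 2.25.

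**Step 5: with an arm-by-visit term,** or with visit-2 A1C adjusted for baseline, the visit-2 contrast is 1.00D whatever k is.

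**The case against.** The strongest reply is that the protocol never commits to a main-effects model. Section 20.1 speaks of models to be examined, leaves room for GLM, GEE or others, and says only that time is accounted for. The single-item structure comes from the power section, which counts variables rather than parameters: group has three levels but counts once, and an interaction is not a new variable. Visit coding and contrasts are also commonly left to a separate SAP, which may exist. And a pilot looking for a preliminary trend need not settle all of this.

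Much of that stands. A reader might infer that the protocol fixes a model without interaction, forces a straight line through time, and will certainly report one to two thirds of the true effect. The documents do not support this:
- The interaction is unlisted, not excluded.
- Linear time is not stated, and the three named visits fit categorical coding equally well.
- The one-to-two-thirds range needs A1C level as outcome and equal visit weights.
- The listed model also contains adherence, which the interventions are meant to change, and quality of life. Conditioning on them can move the group coefficient, and that was not computed.

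Nor is it right that persistence cannot be separated from the 90-day effect. Section 4.0 defines the two outcomes separately; what is missing is a model that delivers them.

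The reply does not remove the mismatch. The text pairs a 90-day outcome with month-6 data, and its one explicit predictor list supplies no term that isolates day 90. That is a conflict in what is written, not merely detail left for later.

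**Conclusion.** The point holds in conditional form. Followed as listed, the primary model's group coefficient does not estimate the visit 1 to visit 2 effect that section 4.0 names as primary. Its size relative to that effect depends on choices the protocol leaves open: 0.33D to 0.67D for A1C level with equal weights, 0.50D to 1.00D for change scores, and lower than the first range under AR(1). All of these take k from 0 to 1 and leave out adherence and quality of life. The loss of efficiency against a baseline-adjusted visit-2 contrast is about 1.3 to 14 times the sample for an assumed rho of 0.3 to 0.7. No single factor should be quoted as the bias of this trial. The wording should be settled before analysis, because it decides what the primary result means.

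**What to change.** State the primary model in section 20.1, and align the predictor list in section 20.2 with it:
- **Outcome:** A1C at visits 2 and 3.
- **Terms:** visit-1 A1C as covariate, arm with three levels (two indicators), visit as categorical, and arm-by-visit.
- **Correlation:** within-participant correlation between visits 2 and 3.
- **Primary estimates:** each intervention arm minus control at visit 2.
- **Secondary estimates:** the same contrasts at visit 3, for the 180-day A1C outcome and Hypotheses 3 and 7.

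The cost is wording only. The planned visits already supply every A1C value the model needs.
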